Do probiotics modulate the intestinal microbiome in extremely premature infants?

Principle Investigator: [name]

REB16-0542

October 11, 2017

Project Title: Do probiotics modulate the intestinal microbiome in extremely premature infants?

Project Type: Primary – Research
Secondary – Clinical care

Principal Applicant (PA): [name] (Concept, literature review, study design, drafting application)
Co-Principal Applicant: [name] (Concept, study design and statistics, drafting application)

Collaborators: [name] (Microbiome Research Scientist)
[name] (ACHRI - Sample analysis)
[name] (MSc student in Microbiology)
[name] (Infection prevention and control)
[name] (Epidemiology and data analysis)
[name] (ACH/FMC pharmacists: product management)

Project Summary:

The gut microbiome plays a significant role in balancing the inflammatory system in the immature gut. A breakdown in this balance with altered colonization of the microbiota in very low birth weight (VLBW) preterm infants is associated with increased feeding intolerance, NEC and sepsis. Probiotics are proposed to normalize microbial populations and decrease intestinal disease in preterm infants. There is limited data linking clinical outcomes with the biology of probiotics. We aim to study the colonization of the GI tract with probiotic species contained in a specific probiotic blend – Florababy – in VLBW preterm infants.

Stool microbiome will be analyzed at 4 time points in 2 groups (one given Florababy and the other no) of infants less than 1000g birth weight and < 29 weeks gestation. A comparison of stool microbiome analysis and the incidence of feeding intolerance and time to reach full feeds in the two groups will be made.

1. What you want to do.

Research question

Does Florababy change the gut colonization pattern in a measurable way in a population of very premature neonates?

Hypothesis:

Florababy probiotics can multiply in the gut and change the colonization pattern of the premature intestinal tract in a measurable way.

Primary outcome: difference in stool microbiome after 4 weeks of Florababy or compared to infants who didn't receive Florababy.

Secondary outcomes: i) difference in stool microbiome 1week after the study drug administration is stopped.

ii) incidence of feeding intolerance and time to reach full feeds.

3. Why this is important.

At a glance:

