Florababy is a 5 strain proprietary probiotic blend produced by Renew Life Canada. It contains 4 billion total CFU of 4 *Bifidobacterium* species (*Breve, bifidum, infantis and longum*) together with *Lactobacillus rhamnosus*. The non-medicinal ingredients are maltodextrin and ascorbic acid. Florababy has been used for only a few years in neonates in Canada. A recently published retrospective cohort study compared data from 17 months before and after introduction of Florababy in a level III NICU for all infants less than 32 weeks gestational age at birth (32). It showed a positive impact on NEC stage 2 or more from a baseline of 10% in infants less than 32 weeks, double the current rate in Calgary. The amount of breastmilk feeding in that cohort is not specified. There was no impact on health care associated infections.

3.3 Biology of probiotics and relation with effects – gaps in knowledge.

The above underscores the need for specific product trials in this population as well as the pressing need for markers and biological understanding. A lot of the limited data concerning the fate of probiotics in preterm infants may not be applicable to current NICU care and feeding practices or was generated before latest genomics technology was available (33-43). The percentage of infants and interval of time in which specific probiotic strains are established in the gut, any differences between strains, differences within a population fed fresh breastmilk and correlation with clinical effects including tolerance of enteral feeds and time to reach full feeds are very important aspects. They need to be clarified for contemporary practices, with best methods, in order to assess and optimize the use of probiotics in the neonate. Using meta-analysis to advocate for an intervention when the biological pathways were not clear has been a source of error before in medicine (44).

3.4 Definition of Feeding Intolerance.

Feeding intolerance will be defined as the inability to digest enteral feedings associated with: i) gastric residual volumes of more than 50% of the volume of the previous feed, ii) abdominal distention and/or emesis, iii) disruption of the baby's feeding plan (decrease, delay or discontinuation of enteral feedings).

4. How you are going to do it.

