4.3 Sample Size and feasibility

A total of 100 infants of birth weight <1000g are born annually and admitted to FMC NICU.

Assuming that 80% of parents' consent to their infant's participation in the study, it will be feasible to complete enrollment of 60 babies in the first year of the study. This study will randomize 30 infants to be given probiotics and 30 infants be in the control group where no probiotic given. The 2 groups will be matched by gender, gestational age +/- one week, birth weight +/- 100g, SGA vs AGA/LGA status and type of delivery.

A sample size of 30 infants per group will allow for a power of 0.8 and an alpha of 0.05 for a two-tailed Wilcoxon-Mann-Whitney test to detect a 0.7 effect size when comparing relative abundance of stool probiotic microbial species in the group given Florababy versus the one given placebo, conservatively assuming a background logistic distribution (G-Power 3.1 software).

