4.4 Variables collected

- a) Demographic variables: Gestational age, birth weight, head circumference at birth, gender, mode of delivery, singleton/multiple and rank, maternal administration of corticosteroids and antibiotics.
- b) Clinical variables: Apgar scores, umbilical cord pH and base excess, first patient blood gas pH and lactate, day of life at start of feeds and at start of study, total days of study drug, antibiotic use during NICU, use of inotropes and vasoactive substances, steroids and medical and/or surgical treatment for PDA, type of feeds during NICU and at discharge.

- c) Outcome variables: mortality; total days of TPN, total days NPO and number of separate NPO events; age, head circumference and weight at discharge home; diagnosis of: feeding intolerance, time taken to reach full enteral feeds (at least 150ml/kg/day), suspected NEC, NEC, cow milk protein allergy, late onset sepsis, BPD, ROP.

4.5 Study protocol.

Infants will be identified within 24 hours of birth and parents will be approached for informed consent.

Once consent is obtained, subjects will be randomly assigned in blocks of 4 to receive either Florababy probiotics orno. Investigators will conduct the randomization using a computer-generated table of random numbers generated at the University of Calgary.

Preparation and Administration of Study Drug

The study probiotic will be started after the first stool sample is obtained and after informed parental consent. Very small amounts of breast milk/colostrum (0.1ml to 0.2ml every 4 hours) are usually given to all premature babies within the first 48 hours of life. Actual feeds of breast and/or human milk (donor milk) are initiated from 72 hours onwards (starting at 10ml/kg/day and increasing slowly thereafter). The study probiotic (at a dose of 0.5g per day) will be started at or after 72 hours of life. It will be administered in 1 ml of sterile water prior to a feed.. No drug will be given to infants in the control group. If the infant is placed NPO, the study drug will be stopped and restarted together with refeeding.

The study probiotic will be given until 34 weeks corrected gestational age.

Sample collection

Nurses will collect the stool samples at 4 time points: prior to, two weeks and four weeks after probiotic administration is commenced, and one week after it is stopped. Stool samples for the control group will be done at a matched feeding and gestational age time points.

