Sequences will be processed with the UPARSE pipeline as implemented in USEARCH v 8.0.1623.⁴⁶ Details for each processing step are outlined. For quality filtering the forward and reverse 16S PCR primers along with any sequencing adapter will be trimmed off the raw reads using cutadapt v1.8. Following this the forward and reverse reads will be overlapped to reconstruct the full amplicon. This will be done using the fastq_mergepairs option in USEARCH v 8.0.1623. Following this the reads will be quality filtered using the maximum expected error method and then truncated at a length of 173 base pairs. Sequences will be dereplicated, where identical reads are merged and counts of these reads are retained, with vsearch v1.1.3

hosted on GitHub (“<https://github.com/torognes/vsearch>”). Singleton reads will be filtered out with vsearch prior to clustering. The remaining sequences are then clustered into groups of 97% identity, designated as Operational Taxonomic Units (OTUs) with the cluster_otus command in USEARCH v 8.0.1623. To construct an OTU table the filtered reads, with singletons included, were searched against the clustered OTU sequences with usearch_global in USEARCH v 8.0.1623.

Taxonomy will be assigned to each of the representative sequences using the RDP Naïve Bayesian Classifier v 2.2⁴⁷ as implemented in Qiime 1.9.0⁴⁸ using the most recent version of the Greengenes database⁴⁹. The RDP classifier uses a bootstrap procedure to assign confidence values to the taxonomic assignments at each level of the taxonomy. The OTU sequences will be aligned with PyNAST, a flexible tool for aligning sequences to a template alignment⁵⁰. Gaps in the alignment will be removed using Qiime’s ‘filter_alignment.py’, and a phylogeny constructed using FastTree, a tool for inferring phylogenies for alignments with up to hundreds of thousands of sequences⁵¹, using default parameters. All remaining analysis will be done in R, a programming language and software environment for [statistical computing](#) and graphics (R Core Team, 2015) using functions from phyloseq⁵² DESeq2⁵³ and vegan.

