The diversity within each sample, also known as α diversity, will be measured using the Shannon index. This is a measure of both the organismal richness of a sample and the evenness of the organisms' abundance distribution⁵⁴. A two-sided Mann-Whitney test (with False Discovery Rate multiple test correction) will be used to determine if there were significant differences in Shannon diversity between cases and controls.

Diversity between samples (β -diversity) will be evaluated using weighted UniFrac, a rank-based ordination method and visualized with Non-metric Multidimensional Scaling (NMDS). β -diversity represents the explicit comparison of microbial (or other) communities based on their composition or relative abundance. β diversity metrics thus assess the differences between microbial communities. To test whether there are significant differences in community structure between groups the UniFrac distance matrix will be tested with permutational multivariate ANOVA (PERMANOVA) implemented in the adonis function in the vegan R package. Differential abundance of individual OTUs between groups will be assessed using generalized linear models with a negative binomial distribution as is used commonly for RNA-seq⁵³. The similarity in data structure between RNA-seq and 16S allow us to adapt already mature methods⁵⁵. This analysis will be performed in DESeq2 v1.8.1 using default parameters.

5. Why you/your group should do it (relevant prior experience and skills, collaborators for technical gaps, preliminary data showing feasibility):

[name] has a lifelong interest and expertise as well as publications in neonatal GI pathophysiology and NEC.

[name] has completed a year of supplementary training in the study of the neonatal intestinal tract in Philadelphia. He is also skilled in study design and statistical analysis and has a Master degree in Epidemiology.

The collaborators include [name], the director of the ACHRI Genomics facility, [name] is a research scientist at -University of Calgary and an expertise in microbiome, [name] (neonatologist and epidemiologist), and [name] – Pediatric Pharmacists.

6. Plans for dissemination or translation of results and plans for next steps in study of topic: The microbiome data will constitute a comprehensive clinical and biological study of probiotic administration in this population. Results will be presented at national and international meetings and submitted for publication.

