Do probiotics modulate the intestinal microbiome in extremely premature infants? Statistical Analysis Plan

Principle Investigator: [name]

REB16-0542

October 11, 2017

Characteristics variables will be analyzed using independent 2-sample t tests when continuous and Pearson χ^2 test when categorical. A P-value of less than 0.05 will be considered significant.

For the microbiome, the diversity within each sample, also known as α diversity, will be measured using the Shannon index. This is a measure of both the organismal richness of a sample and the evenness of the organisms' abundance distribution. A two-sided Mann-Whitney test (with False Discovery Rate multiple test correction) will be used to determine if there were significant differences in Shannon diversity between cases and controls.

Diversity between samples (β -diversity) will be evaluated using weighted UniFrac, a rank-based ordination method and visualized with Non-metric Multidimensional Scaling (NMDS). β -diversity represents the explicit comparison of microbial (or other) communities based on their composition or relative abundance. β diversity metrics thus assess the differences between microbial communities. To test whether there are significant differences in community structure between groups the UniFrac distance matrix will be tested with permutational multivariate ANOVA (PERMANOVA) implemented in the `adonis` function in the `vegan` R package. Differential abundance of individual OTUs between groups will be assessed using generalized linear models with a negative binomial distribution as is used commonly for RNA-seq. The similarity in data structure between RNA-seq and 16S allow us to adapt already mature methods. This analysis will be performed in DESeq2 v1.8.1 using default parameters.

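### The Mann-Whitney test of probiotic-species abundance that justifies 30 infants per arm is not among the planned analyses, so the stated power of 0.8 belongs to none of them

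*Protocol*

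**What the plan says.** **Sample size.** Protocol section 4.3 plans 30 infants per arm. Its only statistical justification is a "two-tailed Wilcoxon-Mann-Whitney test to detect a 0.7 effect size when comparing relative abundance of stool probiotic microbial species", with power 0.8, alpha 0.05 and a logistic parent distribution.

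**Outcome.** The opening section of the protocol gives "Primary outcome: difference in stool microbiome after 4 weeks of Florababy". It names no taxon. The hypothesis in the same section has two parts: that the Florababy organisms multiply in the gut, and that they change the colonization pattern.

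**Planned tests.** The Bioinformatic analysis part of protocol section 4.6 and the SAP list the same three microbiome analyses:
- Shannon index: "A two-sided Mann-Whitney test (with False Discovery Rate multiple test correction) will be used to determine if there were significant differences in Shannon diversity".
- Weighted UniFrac distances, tested by PERMANOVA.
- OTU abundance: "Differential abundance of individual OTUs between groups will be assessed using generalized linear models with a negative binomial distribution", run in DESeq2 with default settings.

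**Ingredients for the powered test.** Section 3.2 lists the five product organisms (four *Bifidobacterium* species and *L. rhamnosus*). Section 4.6 says "Taxonomy will be assigned to each of the representative sequences". Section 4.5 sets four stool samples: "prior to, two weeks and four weeks after probiotic administration is commenced, and one week after it is stopped".

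**The concern.** A sample-size calculation supports a trial only if the test it describes is carried out. Someone who followed the SAP exactly would never make the comparison on which the trial was sized. That comparison also bears most directly on the first part of the hypothesis, that the given organisms establish themselves. Shannon diversity does not say which organisms are present. PERMANOVA can show that communities differ without showing that the product organisms increased.

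Two things are at stake. A reader could credit a planned analysis with 80% power that was calculated for a different one. And because the powered comparison has no analysis text, its remaining detail, how five organisms are combined into one quantity, could be settled after the data are seen.

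**Working it through.** **Step 1: reproduce the plan's figure.** Inputs from protocol section 4.3: n = 30 per arm, standardised effect d = 0.7, two-sided alpha 0.05, logistic parent. The method is the noncentral t power of a two-sample test, with n inflated by the asymptotic relative efficiency (ARE) of the rank test.

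- ARE for a logistic parent = π²/9 = 1.097
- Effective n per arm = 30 × 1.097 = 32.9 (total 65.8)
- Noncentrality = d × √(effective n / 2) = 0.7 × √(32.9 / 2) = 2.84
- Degrees of freedom = 65.8 − 2 = 63.8; critical value = 2.00
- Power = **0.798**

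Direct simulation of the Mann-Whitney test on logistic data (20,000 runs) gives 0.783. The protocol's 0.8 is reproduced. It does depend on the parent distribution and on complete samples: a normal parent (ARE 3/π = 0.955) gives 0.740, and 27 rather than 30 infants per arm with a 4-week sample gives 0.754.

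**Step 2: look for that test in the analysis text.**

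| Planned analysis | Quantity | Is it the powered test? |
|---|---|---|
| Mann-Whitney, FDR-corrected | Shannon index | Same test, different endpoint |
| PERMANOVA | Weighted UniFrac distances | Whole community; no product taxon isolated |
| DESeq2 negative binomial model | Each OTU | Different test; no target taxa |
| qPCR panel (section 4.6) | Listed bacterial groups | No product organism listed, and no test named |

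None is a Mann-Whitney test of probiotic-species abundance. The 0.798 in Step 1 belongs to one test at 0.05 on one quantity, so it cannot be carried over to any row.

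**Step 3: what is open in the powered comparison.**
- Time point: the primary outcome points to the 4-week sample.
- Taxonomic level: section 4.3 says species, and section 3.2 lists them.
- Pooling: not stated. The effect of 0.7 could refer to a sum over the five organisms or to each one separately.

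**Step 4: power of the repaired test.** If the sum is taken over the product species and d = 0.7, power is the 0.798 of Step 1. If only genera can be resolved, background *Bifidobacterium* and *Lactobacillus* may dilute the effect. The documents give no figure for this, so the lower values of d are assumptions:

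| Standardised effect d | Noncentrality (d × √(32.9 / 2)) | Power |
|---|---|---|
| 0.7 | 2.84 | 0.80 |
| 0.6 | 2.43 | 0.67 |
| 0.5 | 2.03 | 0.51 |

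**The case against.** The strongest reply is that little is lost. The primary outcome is a difference in the microbiome as a whole, and PERMANOVA tests that directly. Section 4.3 already fixes the test, sidedness, alpha, endpoint and arms, so the comparison is defined and was simply not carried into the analysis text. The OTU model does look at abundance and could pick up product organisms.

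Most of this stands. PERMANOVA is unaffected, the comparison is largely specified, and only the pooling rule is clearly missing. It would also be wrong to say that abundance as such is ignored: weighted UniFrac uses it at community level, and qPCR measures several groups. The gap concerns the abundance of the probiotic species.

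A reader might go further and infer that the OTU model will probably miss the effect because many OTUs are tested. The documents do not support that. They give no number of OTUs, no number belonging to the product, no effect size per OTU and no dispersion. Any figure built from rank tests would not describe a negative binomial model. A large enough effect could be found by the OTU model as well.

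What the reply does not answer is that the test used to justify 30 per arm is absent from both analysis texts.

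**Conclusion.** The point holds as a mismatch between the sample-size section and the analysis plan. The stated power of 0.8 is correct for the test described (0.798 on the protocol's own assumptions), but no planned analysis is that test, and the figure does not transfer to the OTU model. The size of any loss cannot be computed from the documents.

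This finding rests only on comparing section 4.3 with section 4.6 and the SAP; it needs no assumption about the data. It does not show that the trial is too small, that the sample-size arithmetic is wrong, or that the primary outcome lacks a test. Its weight is modest: a repair worth making because it costs almost nothing, with no bearing on the validity of the PERMANOVA result.

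**What to change.** Add one comparison to the SAP, for example:

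> In the 4-week sample, the summed relative abundance of OTUs assigned to the five product species will be compared between arms by a single two-sided Mann-Whitney test at 0.05, outside the FDR family. If the 16S taxonomy does not resolve these species, the sum of *Bifidobacterium* and *Lactobacillus* will be used. This is the powered key secondary test of the colonization hypothesis. PERMANOVA at 4 weeks is the test of the primary outcome.

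Repeat the same sum, as secondary, in the post-stop sample. This matches the first secondary outcome, "difference in stool microbiome 1week after the study drug administration is stopped". It also helps with interpretation: an infant born at 28 weeks + 6 days who starts at 72 hours is at 33 weeks + 2 days at the 4-week sample (28+6 plus 3 days plus 28 days), still within planned dosing to 34 weeks. That sample cannot separate organisms that multiplied from organisms just swallowed. Infants who start later may differ. Shannon diversity and the OTU model stay as they are.

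**Cost.** No new sample, assay or procedure for the infants, because sequencing and taxonomy are already planned for all samples. The downside is one more test at 0.05 beside PERMANOVA, which the key secondary label makes plain. If the genus sum has to be used, it counts non-product organisms in both arms. Power then stays at 0.80 only if the effect is still 0.7, and a positive result shows that the genera are more abundant, without showing that the product strains are present.

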4.4 Variables collected

- a) Demographic variables: Gestational age, birth weight, head circumference at birth, gender, mode of delivery, singleton/multiple and rank, maternal administration of corticosteroids and antibiotics.
- b) Clinical variables: Apgar scores, umbilical cord pH and base excess, first patient blood gas pH and lactate, day of life at start of feeds and at start of study, total days of study drug, antibiotic use during NICU, use of inotropes and vasoactive substances, steroids and medical and/or surgical treatment for PDA, type of feeds during NICU and at discharge.

- c) Outcome variables: mortality; total days of TPN, total days NPO and number of separate NPO events; age, head circumference and weight at discharge home; diagnosis of: feeding intolerance, time taken to reach full enteral feeds (at least 150ml/kg/day), suspected NEC, NEC, cow milk protein allergy, late onset sepsis, BPD, ROP.

4.5 Study protocol.

Infants will be identified within 24 hours of birth and parents will be approached for informed consent.

Once consent is obtained, subjects will be randomly assigned in blocks of 4 to receive either Florababy probiotics orno. Investigators will conduct the randomization using a computer-generated table of random numbers generated at the University of Calgary.

Preparation and Administration of Study Drug

The study probiotic will be started after the first stool sample is obtained and after informed parental consent. Very small amounts of breast milk/colostrum (0.1ml to 0.2ml every 4 hours) are usually given to all premature babies within the first 48 hours of life. Actual feeds of breast and/or human milk (donor milk) are initiated from 72 hours onwards (starting at 10ml/kg/day and increasing slowly thereafter). The study probiotic (at a dose of 0.5g per day) will be started at or after 72 hours of life. It will be administered in 1 ml of sterile water prior to a feed.. No drug will be given to infants in the control group. If the infant is placed NPO, the study drug will be stopped and restarted together with refeeding.

The study probiotic will be given until 34 weeks corrected gestational age.

Sample collection

Nurses will collect the stool samples at 4 time points: prior to, two weeks and four weeks after probiotic administration is commenced, and one week after it is stopped. Stool samples for the control group will be done at a matched feeding and gestational age time points.

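### A single block size of 4, with past allocations known to the investigators who randomise, makes one third of assignments deducible in advance; varying the block size under an independent list holder is a cheap improvement

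*Protocol*

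**What the plan says.** Protocol section 4.5 (Study protocol) sets one block size: "subjects will be randomly assigned in blocks of 4 to receive either Florababy probiotics" or no probiotic. The same paragraph states "Investigators will conduct the randomization using a computer-generated table of random numbers generated at the University of Calgary". Under the preparation and administration heading it adds "No drug will be given to infants in the control group". On the order of events, "Infants will be identified within 24 hours of birth and parents will be approached for informed consent", and randomisation follows consent.

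Section 4.3 gives the numbers: "This study will randomize 30 infants to be given probiotics and 30 infants be in the control group where no probiotic given". It also says "The 2 groups will be matched by gender, gestational age +/- one week, birth weight +/- 100g, SGA vs AGA/LGA status and type of delivery", without describing how. One phrase there points the other way on masking. The power statement compares relative abundance "in the group given Florababy versus the one given placebo", which conflicts with the no-drug control described in both 4.3 and 4.5. These passages need to be reconciled.

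Neither the Protocol nor the SAP mentions varying block sizes, an independent list holder, or masking of staff.

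**The concern.** With a known block length and known past assignments, the end of each block can be worked out by counting. The fourth infant's arm is always determined, and the third's is determined whenever the first two went to the same arm. Anyone who knows the next arm could let it affect whether, when or how a family is approached. The two groups could then differ at entry in ways that carry into the microbiome contrast, feeding intolerance and time to full feeds.

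This is distinct from concealing the list. A sealed or centrally held list hides future assignments from direct view, but in an open trial with a known fixed block size they can still be inferred from past ones.

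**Working it through.** **The plan's own figure.** The documents give no figure for predictability. Their only design calculation is 80% power for the rank test (4.3). A noncentral t calculation with 30 × π²/9 = 32.9 per group gives 0.7985, and simulating the rank test on logistic data gives 0.783. The stated power is therefore reproduced to within 2 points, and it does not bear on this issue.

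**Inputs.** Block size 4 (4.5); 30 + 30 = 60 infants, so 15 complete blocks (4.3). Assumed: two per arm in each block, one unstratified sequence, and all earlier assignments known when the next family is approached.

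**Share certain in advance, fixed blocks of 4.** There are six equally likely blocks. The probability that an assignment is certain, by position, is 0, 0, 1/3, 1.
- Mean share: (0 + 0 + 1/3 + 1)/4 = 1/3.
- Over 15 blocks: 15 × 4/3 = 20 infants expected (minimum 15, maximum 30, central 95% range 17 to 24).

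**Best guess.** Guessing the less-filled arm is right with probability 1/2, 2/3, 2/3, 1 by position. The mean is (0.5 + 0.667 + 0.667 + 1)/4 = 0.708, against 0.5 by chance.

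**Bias factor.** Suppose enrolled infants are shifted by +d SD when one arm is expected and by −d SD when the other is. Both d and this behaviour are assumptions.
- Acting on any imbalance, the difference in arm means is 2(2g − 1)d, where g is best-guess success: 2(2 × 0.7083 − 1)d = 0.83d.
- Acting only when certain, it is 2 × (certain share) × d = 2 × (1/3)d = 0.67d.

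**Randomly mixed blocks of 4, 6 and 8.** These were simulated over 60 infants for an observer who knows the possible sizes and updates after each assignment.
- Certain share about 2.3%; best guess about 67.8%.
- Acting on any imbalance: 2(2 × 0.678 − 1)d = 0.71d (0.72d in a separate simulation).
- Acting only when certain: 2 × 0.023d = about 0.05d.

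**Effect on a nominal 5% test.** This takes d directly on the outcome scale, which is a worst case. The standard error is √(2/30) = 0.258 SD, and the size is Φ(−1.96 + b/0.258) + Φ(−1.96 − b/0.258), with b the bias. Staff are taken to act on any imbalance, before and after the change:

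| d (assumed) | Fixed 4: bias, size | Mixed 4/6/8: bias, size |
|---|---|---|
| 0.1 | 0.08, 6.2% | 0.07, 5.9% |
| 0.2 | 0.17, 9.9% | 0.14, 8.5% |
| 0.3 | 0.25, 16.2% | 0.21, 13.1% |

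**Sensitivity of the one third.**
- Latest assignment not yet known: only the fourth position can be certain, when the first two match, so (1/3)/4 = 8.3%. With the last two unknown it is 0.
- If the matching in 4.3 were done by stratified blocks (not described): about 31% with 4 equal strata, 28% with 8, 22% with 16 and 11% with 32.

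**The case against.** **The change does little against guessing.** This stands. Best-guess success falls only from 70.8% to about 68%, and for staff who act on any imbalance the bias falls by about 15%. The large reduction applies to certainty, so benefit and harm must be compared under the same behaviour.

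**Varying the sizes achieves little while the investigators hold the table.** This also stands. The lack of any described concealment is the larger gap, and varying blocks helps only if someone else holds the list. The reverse also holds: concealment with a published fixed block of 4 would leave the end of each block deducible.

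**The size figures are worst case.** Correct. They treat a shift in prognosis as a shift in outcome. With an assumed prognosis-outcome correlation of 0.5, size for d = 0.1 to 0.3 under fixed blocks is 5.3% to 7.7%; with 0.3 it is 5.1% to 6.0%. The shift also runs both ways, so d = 0.3 means a 0.6 SD gap between infants enrolled under opposite guesses. The bias should not be read directly against the 0.7 effect size, which concerns relative abundance of probiotic species.

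**The scope for steering is limited.** Partly right. The inclusion criteria are gestation and birth weight, which leave little room for judgement, and the Protocol does not say who approaches parents. Unit staff would see an assignment only once dosing starts, at or after 72 hours, but investigators who randomise know it at once. The one third is lost mainly when consents overlap.

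**Stronger readings.** A reader might infer that enrolment was in fact steered. The documents contain no evidence of that. A reader might also infer that no planned analysis could detect steering. The SAP's comparisons of characteristics between groups could show a large imbalance in a recorded factor, although they have low power at 60 infants, miss unrecorded factors, and remove no bias.

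**Conclusion.** The point holds as a cheap improvement to the design. A single block size of 4, with assignments known to the investigators who randomise, makes 33% of allocations (20 of 60) certain in expectation. That rests on two per arm per block, one unstratified sequence, and full knowledge of earlier assignments; the share is lower, down to about 8% or less, when the latest results are not yet known, and also lower under stratification. This is an opportunity for selection bias created by the plan, and its size depends on d, which the documents cannot supply. Random block sizes remove nearly all of the certainty and only a small part of the guessing.

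**What to change.** In Protocol section 4.5, replace the single block size with randomly varying sizes (for example 4, 6 and 8) and do not state the sizes in the protocol. Have the list and the sizes held by someone already on the project who does not approach parents or judge eligibility, for example the pharmacy that dispenses the product, and release each assignment only after consent is recorded. If enrolment has begun, apply this to the remaining sequence.

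The cost is one regenerated list, a short edit to 4.5 and a small task for the list holder. The arms may differ by up to 4 infants if the last block is incomplete, and guessing is reduced only slightly.
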